4.4. Baseline

Once enrolled in the pilot or RCT, students will begin automated data collection via the BootstrApp Intervention app. The list of baseline (T0) questionnaires is provided in Table 1.

Depending on local school agreements, assessments may be completed during class or at home. To support retention, students can complete the assessments in one sitting or across multiple days. While the target is to complete baseline assessments within 4 days, the window may be extended to 14 days if needed.

4.5. Randomisation

In both the pilot and RCT studies, randomisation will be carried out using individualised, server-based assignment, based on each participant's access code at registration.

Pilot study: For the pilot study each participant will have an equal probability (33.3%) of being allocated to one of the three groups: Emotional regulation intervention group, Inhibitory control intervention group, or the control group.

RCT: For the RCT, each participant will have an equal probability (33.3%) of being allocated to one of three arms: tailored allocation, random allocation, control. This means that participants will have a 66.6% chance of allocation to an active intervention and 33% chance of allocation to the control arm.

Participants allocated to the random allocation arm will have a 50% chance of receiving the emotional regulation or inhibitory control intervention.

In the tailored allocation arm, participants will receive the intervention (targeting emotional regulation or inhibitory control) predicted as most likely to be effective for them by comparing their baseline profile (against the profile of response-predictors developed during the pilot study).

For both the pilot study and the RCT, both participants and researchers will remain blinded to the group allocation to minimise bias. The statistical analysis will be completed on blinded data (allocation A, B or C), with the blinding only being broken when the primary analysis has been completed.

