Study Objective(s)	
The aim of this phase of the study, which incorporates both a pilot study (cohort 2) and an RCT (cohort 3), is to investigate two promising theory-informed candidate preventative interventions, targeting A: emotional regulation and B: inhibitory control, for Problematic Use of the Internet (PUI).
 
For the Pilot study: The primary objective is to use participants' individual characteristics to build models for predicting that predict outcomes for both novel preventative interventions when compared to a control condition (non-interactive provision of information on PUI).
 
The secondary objective is to explore the effectiveness of each preventative intervention compared to a control condition when allocated at random.
 
For the RCT: The primary objective is to evaluate the effectiveness of the predictive models derived from the pilot. We achieve this by comparing the effectiveness of each intervention (i.e., targeting emotional regulation or inhibitory control) when allocated either according to an algorithm derived from individual baseline outcome predictors (tailored arm), or when allocated at random (random arm) versus a control condition (non-interactive provision of information on PUI).
 
The secondary objective is to evaluate and compare the cost-effectiveness and cost utility of both allocation methods (tailored, random), investigating feasibility for large-scale implementation.

Planned Sample Size	3,600 (approximately 400 young people at each site), per cohort.
Participants	Young adolescents aged 12-16

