Importantly, this control condition is informational only, with no interactive or skill-building components. This design is grounded in evidence suggesting that while providing information is a necessary foundation, it is not sufficient to produce meaningful behavioural change on its own (Humphreys et al., 2021). Research consistently shows that effective digital health interventions require interactive, motivational, and skill-based elements to facilitate actual behaviour change (Hou et al., 2014).

Thus, the control condition serves as a credible comparator that accounts for participant engagement and time investment, without introducing the active ingredients known to drive behavioural outcomes.

For a week-by-week transcript of the information given to the control participants please see Appendix C.

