3.3. Study Design

Pilot Study

The Pilot Study is a controlled, individually randomised, observer-blinded, parallel group, three-arm trial. Participants will be allocated to:

Emotional (Affect) Regulation intervention: Strategies for improving affect regulation (affective responses to triggers, worrying), and increase in social skills see section 3.2 and appendix A.

Inhibitory (Executive) control intervention: Strategies for improving executive (inhibitory) control (boundary setting for internet usage, alternative activities, dealing with urges, habits and cognitive bias modification) see section 3.2 and appendix B.

Control: Manualised digital non-interactive information-provision (education) matched with A and B for time investment see section 3.2 and appendix C.

Each intervention will last for four weeks and will be preceded by a two-week baseline assessment period (see tables 1&2), with a post intervention outcome assessment conducted directly at the end of the four weeks intervention (primary end point), and a follow-up for outcome assessment conducted 3-months later (final end point). Figure 1 shows the flow chart detailing study processes, highlighting the stages leading from participant recruitment to final data analysis. At the end of each assessment and intervention time point participants will be asked to provide feedback about their experience of using the app and elements to evaluate the feasibility and acceptability of the app.

Outcomes: The full list of outcome measure assessments including the period of mobile sensing is shown in table 1 and further details about each assessment and mobile sensing variable can be found in section 6.1.1. The primary main outcome measure assessment for both the pilot study and the RCT will be PUI severity as measured using the PIUQ-SF-9 (Demetrovics et al., 2008). Outcomes will be assessed digitally via a series of self-report questionnaires after sending out push-notifications for invitation as well as reminders in case of non-completion. Additional outcome data is collected via the Dragon Game app, which includes cognitive assessment tasks for affect regulation and inhibitory executive control. As a complementary modality for secondary outcome assessment, smartphone behaviour (data tracking) will also be measured.

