Figure 2. Flow diagram of the optional extension phase. Participant will initially consent to the extension phase during the consent process of the Pilot study. At the 3-month follow-up participants who consented to take part in the extension phase will be sent a push notification through the app to confirm their assent to continue. The 3-month follow-up assessments will be used as a baseline measure for the extension phase.

Randomised Control Trial

The RCT is a controlled, individually randomised, observer-blind, parallel-group, three-arm trial. Participants will be allocated to:

Tailored Arm: Tailored allocation to the Emotional regulation intervention or the Inhibitory control intervention based on prediction of outcome algorithms developed in the Pilot Study.

Random Arm: Random allocation to the Emotional regulation intervention or Inhibitory control intervention.

Control Arm: non-interactive information-provision (education) on safe and effective use of the internet.

Each intervention will last for four weeks, preceded by a two-week baseline assessment (see tables 1&2) period, with a post intervention outcome assessment conducted directly at the end of the four weeks intervention (primary end point), and a follow-up for outcome assessment conducted 6-months later (final end point). Outcomes will be assessed digitally via a series of self-report questionnaires after sending out push-notifications for invitation as well as reminders in case of non-completion. Additional outcome data is collected via the Dragon Game app, which includes cognitive assessment tasks for affect regulation and inhibitory executive control. As a complementary modality for outcome assessment, smartphone behaviour (data tracking) will also be measured. Figure 3 shows the flow chart detailing study processes, highlighting the stages leading from participant recruitment to final data analysis.

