4.2. Recruitment

Each of the nine participating countries has established partnerships with local schools previously involved in the assessment app study, with agreements to continue in the BootStRaP project. At each school, at least one teacher and one student serve as BootStRaP Ambassadors, supporting engagement and retention throughout the pilot and RCT phases. Additional schools will be recruited if needed.

Where available, student organisations will also be engaged to support recruitment. Locally appropriate incentives (e.g. lotteries, competitions, or honoraria) will be used to encourage participation, tailored to each centre's context.

Local researchers and BootStRaP Ambassadors will introduce the study to students, explain its purpose, and demonstrate the BootstrApp Intervention app and Dragon Game app, which will be installed on students' smartphones. Students will have the opportunity to ask questions during these sessions.

Parents or guardians will receive an information pack and be invited to attend at least one session to learn more and ask questions. Participation requires parental consent and student assent. A holding page on the BootstrApp will require a unique code, provided during the information session, to confirm consent, assent, and school affiliation.

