8.1.1. Risk-Benefit Assessment

The pilot study and RCT will build on the findings of the assessment study, offering unprecedented insights into the psychological mechanisms underlying PUI risk, the early detection of at-risk adolescents, and effective preventative interventions. The BootStRaP project aims to develop evidence-based policy recommendations that could significantly contribute to the prevention of problematic internet use across Europe.

The study's robust recruitment strategy, which includes adolescents from nine European countries with diverse genders, socioeconomic backgrounds, and geographical areas (rural and urban), enhances the generalisability of the results.

The risk to participants is expected to be minimal, as the health lifestyle and well-being interventions are designed to prevent PUI, a behavioural issue not a clinical condition, rather than to treat a medical disorder. The study purpose is clearly explained to participants beforehand, including information on the questions asked and potential interventions offered.

Participation is entirely voluntary, and participants can withdraw at any time without providing a reason. If emotional distress arises, the study app includes a dedicated help submenu, guiding participants and, where appropriate, their parents to local mental health support services for children and adolescents.

The study places a strong emphasis on data protection, confidentiality, and anonymity, as detailed in Data Management (Section 6.2) and Data Protection and Participant Confidentiality (Section 11).

The pilot study and RCT are expected to benefit participants by:

- Reducing their risk of PUI.
- Enhancing emotional regulation and inhibitory control strategies, depending on the allocated intervention.

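### The blinding claim goes further than the design supports: participants can probably tell active from control and report the outcome themselves, and the RCT's A/B/C analyst blind cannot last through primary question 3

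*Protocol*

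**What the plan says.** **Blinding claims.** Section 4.5 states, for the pilot and the RCT, that "both participants and researchers will remain blinded to the group allocation to minimise bias". It adds: "The statistical analysis will be completed on blinded data (allocation A, B or C"), with the code broken only once the primary analysis is finished. The design label is narrower. Section 3.3 says "The RCT is a controlled, individually randomised, observer-blind, parallel-group, three-arm trial", and the Study Summary, the pilot part of 3.3 and section 6.1 use the same observer-blind label.

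**What each arm receives.** Section 3.2 says "this control condition is informational only, with no interactive or skill-building components". Section 4.6 has controls read material while the other arms complete tasks, and the introduction in Appendix C tells controls to expect a brief post on alternate days. Appendices A and B give the active arms an astronaut story, games, coins, challenges and personalised feedback.

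**What pupils know beforehand.** Section 8.1.1 says the study purpose is explained in advance, "including information on the questions asked and potential interventions offered". Section 3.4.1 recruits by class, and 4.5 randomises individuals.

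**Who measures the outcome.** Section 3.3: "Outcomes will be assessed digitally via a series of self-report questionnaires". Section 11.1 says participants complete the electronic CRF themselves.

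**What the RCT must answer.** Section 6.3.2 lists three primary questions: (1) pooled active versus control, 2:1; (2) tailored versus random; (3) emotional regulation versus inhibitory control, whatever the allocation method.

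**The concern.** A blinding statement tells readers how far to trust a self-reported difference. Here the conditions look and feel different, classmates can be in different arms, and pupils know beforehand which programmes are on offer. The person who fills in the primary questionnaire is the person who received the programme. An observer-blind label protects nothing when no separate observer exists.

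The comparisons at stake are RCT question 1 and the pilot's active-versus-control comparisons. If active participants shade their answers because they know they did the interactive programme, the shift enters the treatment effect directly. With samples this large, a small shift can be enough for significance.

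The analyst blind is a separate matter. Section 4.5 promises that it lasts until the primary analysis is complete, but one of the three primary questions uses a variable that reveals which code is control.

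**Working it through.** **1. Can the stated blinding hold, role by role?**

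| Role and comparison | Claim in 4.5 | What the design provides |
|---|---|---|
| Participant, active v control | blind | Interactive programme v reading only; programmes described beforehand; classmates in different arms. Recognition is likely, by inference |
| Participant, tailored v random | blind | Both arms receive the same two programmes. Masking is plausible |
| Outcome assessor | observer-blind (3.3, 6.1) | The participant; no separate observer |
| RCT analyst, questions 1 and 2 | codes A, B, C | Feasible: fit a three-level model, produce every one-versus-two and every pairwise contrast, attach labels afterwards |
| RCT analyst, question 3 | codes A, B, C | Not feasible: intervention received is defined in two codes only, so the third is control |
| Pilot analyst | codes A, B, C | Feasible for pairwise contrasts: codes map one-to-one to groups |

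**2. Does question 3 expose more than control?** Possibly. In the random arm the expected share receiving emotional regulation is 50% (section 4.5). With 838 participants the standard error is √(0.25/838) = 0.0173, giving a 95% range of 46.6% to 53.4%. If the algorithm sent, say, 60% of the tailored arm to one programme (an assumed figure), that arm would lie (0.60 − 0.50)/0.0173 = 5.8 standard errors from 50%. The tailored and random codes would then be recognisable too.

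**3. The plan's sample figures (section 3.4.2).** For d = 0.3, α = 0.05 (two-sided assumed) and 80% power, the t-based solution is 175.4, rounded up to 176 per group. Then 176/0.3/0.7 = 838.1 and 3 × 838 = 2,514. These reproduce and are not in dispute.

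**4. How much could a reporting shift matter for question 1?** Assumptions: no true effect, SD 1, independent observations, and a differential shift b in the active arms. The documents give no value for b, so a range is shown.

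- SE = √(1/n_control + 1/n_active)
- P(significant) = 1 − Φ(1.96 − b/SE) + Φ(−1.96 − b/SE)

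All completers: 0.70 × 838 = 586.6 control and 2 × 586.6 = 1,173.2 active, so SE = √(1/586.6 + 1/1,173.2) = 0.0506.

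High-risk completers, the group on which 3.4.2 bases its calculation: 176 control and 352 active, so SE = √(1/176 + 1/352) = 0.0923.

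| Assumed shift b (SD) | All completers | 176 high-risk per arm |
|---|---|---|
| 0 | 5.0% | 5.0% |
| 0.05 | 16.7% | 8.4% |
| 0.10 | 50.7% | 19.1% |
| 0.15 | 84.3% | 36.9% |

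A shift of 0.10 SD is one third of the planned d = 0.3.

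**The case against.** **Participants.** All arms use the same app at a similar pace, and section 3.2 describes the control as time-matched and credible. Its introduction promises useful advice, so a pupil need not recognise it as control. The information sheets are not in the document, so how the arms are described to pupils cannot be judged. This stands in part: unblinding is an inference, not something the protocol states. But time-matching deals with attention, not with knowledge of the condition, and it does not support an unqualified claim that participants remain blind. Comparing phones could also spread intervention content to controls and pull the estimate towards zero, so the net bias need not favour the intervention.

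**Stronger readings that the documents do not support.**

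- *The analyst blind fails everywhere.* It does not. RCT questions 1 and 2 and the pilot's pairwise comparisons can run as contrasts on codes. Section 6.3.2 takes the questions in turn and lists question 3 last.
- *The protocol publishes the code.* The Study Summary does say "targeting A: emotional regulation and B: inhibitory control", but those letters name the interventions. Nothing links them to the masking codes, and the RCT arms are tailored, random and control.
- *Pupils see the active content before enrolment.* Section 4.2 has researchers "explain its purpose, and demonstrate the BootstrApp Intervention app and Dragon Game app". That app also hosts assessments and control material, and the text does not say that intervention modules are shown.
- *Class visits show that researchers know allocation.* The visits in 4.7 need no such knowledge, and assignment is server-based.
- *Active participants are all told that their use is a problem.* Feedback depends on the score, and low scorers are reassured. The control material also covers unhelpful patterns and alternatives.

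**Conclusion.** The point holds in this form. For active versus control, participant blinding is not assured by the design, and the observer-blind label describes an assessor the trial does not have. In the RCT the A/B/C blind cannot last through all three primary questions, because question 3 identifies the control code. That second part follows from the structure of the question and needs no assumption. The first rests on an inference from the programme content, the prior information and the shared classes.

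The size is conditional. Under assumed shifts of 0.05 to 0.15 SD and no true effect, the chance of a significant question 1 rises from 5% to about 17–84% with all completers, or about 8–37% with 176 high-risk completers per arm. These figures show sensitivity; they do not predict the bias. Tailored versus random is much less exposed, since both arms receive the same two programmes. The trial remains viable, but its blinding statement should be corrected.

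**What to change.** 1. **Restate who is blind.** In the Study Summary and sections 3.3, 4.5 and 6.1, replace the observer-blind label and the statement on participants and researchers. Say that participants are not assured to be blind between active and control and self-report the outcome, and that only tailored versus random is masked to them. Interpret question 1 and the pilot's active-versus-control results accordingly.
2. **Replace the A/B/C rule for the RCT.** Either finalise the primary-analysis code on scrambled allocations and run it once on the true ones, or run questions 1 and 2 as contrasts on codes and release intervention received only for question 3.
3. **Optional.** Add one arm-guess item at T1, and report the mobile-sensing outcome as supportive evidence for question 1. It should not be a condition for accepting the self-report result: section 6.1.1 says the PIUQ-9 covers obsession, neglect and control disorder, and a true change there need not appear as less phone use.

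**Cost.** Protocol wording, one rule for the order of analysis and, if wanted, one app item. No change to arms or sample size. The stated blinding becomes less favourable, and sensing data will be incomplete on some devices.

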4.6. Intervention

In both the pilot and RCT study interventions (emotional regulation, inhibitory control and control) as described in section 3.2 will be delivered and completed through the app (see table 2 for a breakdown intervention tasks). On average, participants are asked to complete assigned tasks of the intervention (or for the control group, read presented information) every 2 days over a period of 4 consecutive weeks. The tasks will be delivered through the BootstrApp intervention app with participants being notified of a task to complete via automated push notification.

Within the two intervention arms (targeting emotional regulation or inhibitory control), participants are categorised according to their risk for PUI, using the baseline S-CUIS score with scores of ≥ 9 indicating high risk of PUI. Participants at high risk for PUI are given access to additional intervention elements that either address emotion regulation or inhibitory control in the context of problematic Internet use.

4.7. Follow up Procedures

The BootstrApp Intervention app will guide study participants through assessment and intervention blocks, granting access to information about upcoming tasks directly on its home screen. Automatic push notifications will be sent to prompt completion of upcoming questionnaires/intervention tasks. Automated reminders will be dispatched through the app to ensure timely participation. Depending on individual agreements with schools, the young people can have the possibility to complete their assessments in class and local researchers can arrange visits in class or schools together with school ambassadors, to increase motivation and reinforce awareness of the upcoming assessments/interventions. The complete schedule of assessments and interventions including baseline and subsequent assessments is presented in Table 1 and Table 2. Further detailed information about each assessment can be found in section 6.1.1 and about the interventions in section 6.1.2.

4.8. End of Study

The study will conclude once all participants have completed their assessments and interventions, or when the final assessment window closes. The University of Hertfordshire (UoH) will notify study centres when this point is reached.

End-of-study declarations will be submitted to local ethics committees in accordance with their regulations (e.g. within 90 days, where applicable).

To acknowledge their participation, students who complete the minimum dataset will receive a certificate and compensation at the end of the 3-month (pilot) or 6-month (RCT) follow-up. Additional compensation will be provided for those in the pilot extension. Centres may offer vouchers or prize draws, with formats tailored to local preferences.

Participants will also have the option to receive feedback via the BootstrApp, either during the intervention (where relevant) or after study completion. Feedback may include screen time, app usage, and selected questionnaire results. Participants can choose to view only their own data or compare it with aggregated group data.

